For subjects entering the 12-month Post-Treatment Follow-Up Period, visits will be conducted either by phone or on-site from Month 1 through Month 12. (Subjects who prematurely discontinue from the Treatment Period prior to the Month 3 Study visit, are not required to have the pelvic ultrasound, MRI [if applicable] or DXA [unless the reason for discontinuation was due to BMD decrease or occurrence of fracture] performed in the Post-Treatment Follow-up Period and will complete the study at the Post-Treatment Follow-up Month 6 visit.) Post-Treatment Follow-up Months 1, 3, 6, 9 and 12 are on-site visits while Post-Treatment Follow-up Months 2, 4, 5, 7, 8, 10 and 11 are Phone Visits.

During the phone visits, site personnel will discuss adverse events, concomitant medications, if applicable, obtain the results of the subject's self-administered urine pregnancy test and will remind subjects of the importance of consistent use of appropriate and effective dual non-hormonal contraception through the Post-Treatment Follow-Up Period. Subjects may begin taking hormonal contraception or Tranexamic Acid (Lysteda, Cyklokapron, Cyclo-f) after completing the Post-Treatment Follow-Up Month 2 Visit and having returned to first full menses in the Post-Treatment Follow-up Period.

Subjects will be required to collect sanitary products for the first full menses in the Post-Treatment Follow-up Period. Subjects will return the sanitary products at a Product Collection Visit within approximately 5 days after cessation of bleeding or spotting.

During the Post-Treatment Month 3 and Post-Treatment Month 6 on-site visits, procedures such as TAU, TVU, MRI (if applicable), DXA, clinical safety labs and pregnancy testing will be performed. At the Post-Treatment Period Month 12 visit, procedures including vital signs, lipid panel, Apolipoprotein A and B and DXA will be performed.

Adverse event and concomitant medication review will be conducted at all visits during the Post-Treatment Follow-Up Period, including the phone visits.

Central Laboratory and Central Imaging Vendors:

DXA, Ultrasound, SIS, MRI (if applicable), safety clinical lab samples including Apo A, and Apo B, endocrine panels, and alkaline hematin will be analyzed/evaluated using central laboratories or vendors. Assays for PK, PD and PG will be analyzed at AbbVie.

Analysis of Menstrual Blood Loss:

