Subjects will be required to collect sanitary products for their first menses with full menstrual flow in the Post-Treatment Follow-up Period. If the subject misses collecting sanitary products for her first full menses, she will be required to collect sanitary products for her next full menses. Subjects will return the sanitary products at a Product Collection Visit within approximately 5 days after cessation of bleeding or spotting. The Post-Treatment UBQ will be administered by Site Staff at each Phone or Site Visit until the subject has returned sanitary products from one full menses in the Post-Treatment Follow-up Period. Once a subject returns sanitary products from a full menses in the Post-Treatment Follow-up Period, the Post-Treatment UBQ no longer needs to be completed.

Subjects who prematurely discontinued from the Treatment Period prior to the Month 3 Study Visit, (e.g., subjects who received < 3 months of study drug), will enter into the Post-Treatment Follow-Up Period, however, the number of procedures/assessments performed in the Post-Treatment Period will be reduced and these subjects will complete

the study at the Post-Treatment Follow-up Month 6 visit (unless the reason for premature discontinuation was due to BMD decrease or an adverse event of fracture). Procedures/assessments should be performed as specified in Appendix C, Study Activities.

Unscheduled Visit and Unscheduled Visits for Delays in Roll-Over

In the event an Unscheduled Visit is necessary during the Treatment or Post-Treatment Follow-Up Period, the site will perform at minimum, the UBQ and an assessment of adverse events and concomitant medications. Unscheduled visits should be limited to when a subject is required to return to the office or off-site facility to repeat a procedure or to conduct a procedure to assess safety and the visit is not occurring at the same time when other study related-procedures are scheduled to occur. For unscheduled visits when study drug is dispensed (e.g., to replenish lost or damaged study drug), the subject will also be required to have a negative urine pregnancy test result prior to dispensing. Clinical judgment should dictate when other safety assessments (such as vital signs and/or symptom-directed physical examination) should be conducted and should also support the reason for the unscheduled visit.

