- Subjects with ≥ 8% BMD decrease at any location at Month 6 of the Treatment Period are not eligible for entry into the extension study and will instead enter into the Post-Treatment Follow-Up Period and continue with BMD evaluation as illustrated in Figure 4.

[figure not shown]
[figure not shown]

Figure 3. Management of BMD % Decrease at Month 6 of Treatment Period and Eligibility for Inclusion in the Extension Study

Management of BMD for Subjects Entering the Post-Treatment Follow-Up Period

[figure not shown]
For subjects entering the Post-Treatment Follow-Up Period of this study, DXA scans are required at Month 6 and Month 12 of the Post-Treatment Follow-Up Period.

A Post-Treatment Month 6 or Month 12 DXA will not be performed in subjects who prematurely discontinued prior to the Treatment Month 3 visit, i.e., received < 3 months of study drug during the Treatment Period (unless the premature discontinuation was related to BMD decrease or the occurrence of a fracture).

Management of BMD % Decrease at Post-Treatment Follow-up Month 12

Management of subjects with BMD % decrease at Post-Treatment Follow-Up Month 12 is outlined below and illustrated in Figure 4.

Subjects with Post-Treatment Month 12 BMD % decrease of < 3% in the spine, femoral neck and total hip and no decrease in any region from Post-Treatment Follow-up Month 6 to Month 12 will not require a referral to a bone specialist.

Subjects will be referred to a Bone Specialist at Post-Treatment Follow-up Month 12, even if the overall BMD decrease from baseline is < 3%, if they meet the following criteria:

- Subject had Post-Treatment Month 6 BMD decrease compared to baseline in any region and demonstrates further BMD decrease at Month 12 in the same region (between Post-Treatment Month 6 and Month 12) and, subject meets one of the following:
 - Subject was \ge 45 years of age at the time of last dose of study drug in the Treatment Period
 - OR
 - Subject has not had a menses in the past 12 months
- Subjects with Post-Treatment Month 12 BMD % decrease of \geq 3% in the spine, femoral neck or total hip and a T-score < -1.0 OR T-score < -1.5 will be referred to a bone specialist for further management, and will be followed on an individual basis.

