				12-N	Jonth Pos	st-Treatm	ent Follov	12-Month Post-Treatment Follow-Up Period ^a)d ^a					
	Month 1	Month 2	Month 3	Month 4	Month 5	Month 6*	Month 7	Month 8	Month 9	Month 10	Month 11	Month 12	PCV	$\mathbf{PD}^{\#}$
Phone Contact/Phone Visit		x		x	х		X	x		x	Х			
Pelvic Ultrasound ^{(a)} : TVU, TAU			X ^b			X ^b								X ^b
MRI (Subset of Subjects) [@]			X ^b											X ^b
Complete Physical Examination: including weight (W)						X (W)								X (W)
Symptom Directed Physical Examination	Х		Х						Х			X		
Vital Signs	Х		х			x			х			Х	Х	X
DXA Scan						X°						X ^c		Xc
Clinical Safety Labs: Chemistry, Hematology, Lipid Panel and Urinalysis	Х		Х			Х			Х			X ^d		Х
Apolipoprotein A and B	Х		Х			Х			Х			Х		Х
Urine Pregnancy Test ^e	Х	\mathbf{X}^{f}	Х	X^{f}	X^{f}	Х	\mathbf{X}^{f}	\mathbf{X}^{f}	Х	\mathbf{X}^{f}	\mathbf{X}^{f}	Х	Х	Х
Serum Pregnancy Test												Х		Х
Return sanitary products for the first menses in Post-Treatment													X ^g	
Contraception Counseling/Dispense Contraceptives ^h	Х	X	Х	х	Х	Х	Х	Х	Х	Х	Х	X	Х	
PRO UBQ (as Questionnaires applicable)	Xi	X ⁱ	X ⁱ	X ⁱ	X ⁱ	X ⁱ	X ⁱ	X ⁱ	X ⁱ	X ⁱ	X ⁱ	X ⁱ	X ⁱ	X
Adverse Event Monitoring	Х	\mathbf{X}^{j}	Х	Х	Х	Х	Х	Х	Х	Х	Х	Х	Х	х

171

					12-]	Month Po.	st-Treatm	ient Follo	12-Month Post-Treatment Follow-Up Period ^a	od ^a					
		Month 1	Month 2	Month 3	Month 4	Month 5	Month 6*	Month 7	Month 8	Month 9	Month 10	Month 11	Month 12	PCV	$\mathbf{PD}^{\#}$
Ŭ	Concomitant Medication Review	х	Х	х	Х	Х	Х	Х	х	Х	x	x	х	Х	Х
*	Subjects who prematurely discontinue from the Treatment Period prior to the Month 3 Study Visit, i.e., who received < 3 months of study drug, will complete the study at the Post-Treatment Follow-up Month 6 visit.	tue from the visit.	e Treatmer	nt Period p.	rior to the	Month 3 5	study Visi	t, i.e., who	received <	< 3 months	of study d	lrug, will c	omplete th	ie study	at th
#	Subjects who prematurely discontinue after the Post-Treatment Month 6 visit, should only complete procedures and assessments which are required for the Post-Treatment Follow-up Month 12 visit.	ue after the	: Post-Tre	atment Mo.	nth 6 visit	, should or	ıly comple	te procedı	ures and as	sessments	which are	required fo	or the Post	-Treatm	lent

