B	Subjects with a finding of polyp on pelvic ultrasound or MRI at during the Post-Treatment Period will undergo evaluation per standard of care which may include an SIS.	pelvic ultra	sound or l	MRI at dur	ing the Pc	st-Treatmo	ent Period	will under	rgo evaluat	ion per sta	ndard of c	are which	may inclu	le an SI	S.
a. b.	Refer to Table 1, Visit and Assessment Windows, for allowable visit and assessment-specific windows during the Post-Treatment Period. Not required if performed within 2 months prior to PD or if subject prematurely discontinued prior to Treatment Month 3, i.e., received < 3 months of study drug during the Treatment Period.	nent Windor months prio	ws, for alle or to PD of	owable vis. r if subject	it and asse premature	essment-sp ely discont	ecific wind	dows durii r to Treatn	ng the Post nent Montl	-Treatmen h 3, i.e., re	t Period. ceived < 3	months of	study dru	g during	5 the
	DXA Scan is not required if subject prematurely discontinued prior to Treatment Month 3, i.e., received < 3 months of study drug during the Treatment Period (unless the premature discontinuation was related to BMD decrease or the occurrence of a fracture).	prematurel ed to BMD	ly disconti decrease	inued prior or the occu	to Treatn urrence of	nent Month a fracture)	ı 3, i.e., reı	ceived < 3	months of	study dru	g during th	e Treatme	nt Period (unless t	he
q.	Safety labs at Post-Treatment Follow-up Month 12:	w-up Mont!		Lipid Panel only	ly.										
e.	A positive urine pregnancy test result must be confirmed with a quantitative serum pregnancy test. For any subject who has a positive serum pregnancy test result, a TVU must be performed during the first trimester of pregnancy to assess the gestational age and estimated date of delivery. The site will immediately inform the subject to discontinue study drug and the subject will be discontinued from the study at the point the pregnancy is confirmed.	ilt must be c rimester of ect will be c	confirmed pregnancy fiscontinu	with a que / to assess ed from the	intitative s the gestati s study at	serum pregional age a the point the	nancy test nd estimat he pregnar	. For any ed date of tcy is conf	subject wh delivery. firmed.	o has a po The site w	sitive seruı ill immedi	m pregnan ately infor	cy test resi m the subj	ult, a TV ect to	P,
÷	Home pregnancy test kit will be self-administered at	f-administer	red at hom	home by the subject.	ıbject.										

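### Appendix C and the synopsis end follow-up at Post-Treatment Month 6 for women who stop early because of BMD decrease or fracture, although Section 5.1 exempts them and their Month 12 DXA is still required

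*Protocol*

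**What the plan says.** The point concerns only women who stop study drug before Treatment Month 3 because of BMD decrease or fracture. For all other early stoppers the documents agree on completion at Post-Treatment Month 6.

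- **Section 5.1, Post-Treatment Follow-Up Period.** Early stoppers have reduced procedures and complete the study at Post-Treatment Month 6, "unless the reason for premature discontinuation was due to BMD decrease or an adverse event of fracture". The exception is attached to completion itself. The next sentence sends sites to the schedule: "Procedures/assessments should be performed as specified in Appendix C, Study Activities".
- **Section 5.3.1.1, Management of BMD for Subjects Entering the Post-Treatment Follow-Up Period.** The scan waiver reads: "A Post-Treatment Month 6 or Month 12 DXA will not be performed in subjects who prematurely discontinued prior to the Treatment Month 3 visit", with an exception for discontinuation related to BMD decrease or fracture. These women therefore keep both scans.
- **Appendix C, post-treatment schedule, DXA footnote.** The scan is waived after less than 3 months of "study drug during the Treatment Period (unless the premature discontinuation was related to BMD decrease or the occurrence of a fracture").
- **Appendix C, post-treatment schedule, asterisk footnote on the Month 6 column.** Subjects "who received < 3 months of study drug, will complete the study at the Post-Treatment Follow-up Month 6 visit". No exception is given.
- **Synopsis, Post-Treatment Follow-Up Period.** The exception "unless the reason for discontinuation was due to BMD decrease or occurrence of fracture" is bracketed inside the DXA item. The sentence then ends without qualification: "performed in the Post-Treatment Follow-up Period and will complete the study at the Post-Treatment Follow-up Month 6 visit".

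**The concern.** For the same woman, Section 5.1 says she does not finish at Month 6, while the asterisk footnote and the synopsis say she does. Appendix C also conflicts with itself, since one footnote keeps her Month 12 DXA and another ends her participation about six months before it.

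The footnote is an operative rule, because Section 5.1 sends sites to Appendix C for what to do with these women. If it is followed, two things are lost: a required bone-safety scan, and the Month 12 assessment in Section 5.3.1.1 ("Subjects will be referred to a Bone Specialist at Post-Treatment Follow-up Month 12" when the criteria are met). One of those criteria compares the Month 6 and Month 12 scans, so it cannot be assessed without the second. Section 6.1.4 collects adverse events through Month 6 or Month 12 as applicable, so collection of new events would also stop earlier. These are the women the protocol singles out for longer bone follow-up, in a study with BMD among its stated objectives.

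**Working it through.** The plan states no figure to reproduce. The check compares the clauses and then asks whether visit windows could rescue the scan.

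**1. The clauses side by side**

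| Place | Rule for early stoppers | Where the BMD/fracture exception sits |
|---|---|---|
| Section 5.1 | Complete at Month 6 | On completion |
| Appendix C, asterisk footnote | Complete at Month 6 | Nowhere |
| Synopsis | No DXA; complete at Month 6 | On the DXA only |
| Section 5.3.1.1, Bone Mineral Density (DXA Scan) | No post-treatment DXA; complete at Month 6 | Mid-sentence, after the scans; its reach over completion is ambiguous |
| Section 5.3.1.1, Management of BMD | No Month 6 or Month 12 DXA | On both scans |
| Appendix C, DXA footnote | No DXA | On the DXA |
| Section 5.4.1 | No DXA at Month 6 | On the DXA; silent on Month 12 and on completion |

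The letter of the Appendix C DXA footnote is missing from the text available to me. It sits between notes b and d, and the Month 12 DXA cell is marked c.

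**2. Could a late Month 6 visit capture the Month 12 scan?**

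Inputs: a month is 28 days (Section 1.3, Definition of Terms). Post-treatment visits have a window of ±7 days, and the Month 12 DXA has a window of −15 or +4 days (Table 1). SAP Table 8 uses the same nominal days, 168 and 336, counted from the last dose.

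- Latest in-window Month 6 visit: 6 × 28 + 7 = 168 + 7 = Day 175
- Earliest in-window Month 12 DXA: 12 × 28 − 15 = 336 − 15 = Day 321
- Gap: 321 − 175 = **146 days**

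Both days run from the same origin, so the gap does not depend on which origin a site uses. The Month 12 scan cannot be done at a Month 6 close-out.

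**3. Follow-up lost per woman closed out at Month 6**

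- Nominal time: 336 − 168 = 168 days
- Contacts after Month 6 (synopsis): on-site at Months 9 and 12; by phone at Months 7, 8, 10 and 11. Total 2 + 4 = 6.
- One required DXA and the Month 12 referral assessment

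**4. How many women**

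The documents give no rate. Assuming 0%, 0.25% or 0.5% of about 400 randomized: 400 × 0 = 0; 400 × 0.0025 = 1; 400 × 0.005 = 2. No routine on-treatment DXA is scheduled before Month 6, so an early stop for BMD decrease is unlikely and fracture is the main route.

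**The case against.** The strongest reply is that the documents, read together, give one workable instruction. The asterisk footnote is the general rule for early stoppers. Section 5.1, Section 5.3.1.1 and the DXA footnote in the same table are the specific rule for this subgroup. On that reading a site loses the scan only if it applies one footnote and overlooks another beside it. This stands in part: the intended rule is clear, and the loss is conditional on a site following the asterisk footnote as written. It does not remove the conflict. I found no clause giving the body text precedence over the appendix, and Section 5.1 itself points sites to Appendix C.

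The second objection is that the DXA paragraph of Section 5.3.1.1 is built like the synopsis, so both should be called wrong or both ambiguous. There is a difference. In the synopsis the bracket is confined to one item in a list. In Section 5.3.1.1 the exception interrupts the sentence and can be read to cover completion, at least once the other two places are corrected. An edit there is useful but optional.

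The third is that the group is hypothetical. Women with a screening T-score of −1.5 or lower, or a prior low-trauma fracture, are excluded, and exposure before the stop is under 3 months. That stands, and it limits the weight of the point. Other safeguards also remain: the DXAs at premature discontinuation and Post-Treatment Month 6, follow-up of adverse events to a satisfactory conclusion (Section 6.0), and the follow-up of events ongoing at discontinuation that Section 5.4.1 asks for.

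**Conclusion.** The inconsistency is real and in current text. The asterisk footnote and the synopsis completion clause contradict Section 5.1, and following either removes a scan that Section 5.3.1.1 and Appendix C itself require. It is minor. Per affected woman the cost is one DXA, the Month 12 referral assessment and six contacts. The number of women, 0 to 2, rests on an assumed rate and could well be zero. Even for an affected woman, referral depends on further criteria being met. The primary endpoint, sample size and type I error are untouched. The conflict in wording is certain; the loss of data depends on which clause a site applies.

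**What to change.** Add the same exception in two places, the asterisk footnote to the Appendix C post-treatment schedule and the synopsis completion clause: unless the reason for premature discontinuation was BMD decrease or fracture, in which case the subject continues to Post-Treatment Month 12.

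Optionally, reword the DXA paragraph of Section 5.3.1.1 so that its exception explicitly covers study completion as well as the scans. Section 5.4.1 can stay as it is, since it already carries the exception for the DXA and says nothing about completion. Section 5.1, the Management of BMD text and the Appendix C DXA footnote already agree with the rule.

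This is wording only, for the next amendment or a clarification letter to sites. It adds no visits or scans beyond those Sections 5.1 and 5.3.1.1 already require.

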Appendix D. BI-RADS Classification

The BI-RADS assessment categories are:

- 0 -Incomplete,
- 1 Negative,
- 2 Benign,
- 3 Probably benign,
- 4 Suspicious,
- 5 Highly suggestive of malignancy,
- 6 Known biopsy proven malignancy

Reference: ACR BI-RADS Atlas Fifth Edition. p. 15-8. Available from: https://www.acr.org/~/media/ACR/Documents/PDF/QualitySafety/Resources/BIRADS/01-Mammography/02--BIRADS-Mammography-Reporting.pdf?la=en.¹²

Appendix E. Reason for Study Participation – SAMPLE

We would like to ask you why you have agreed to participate in this clinical research study. I am participating in this research study because (Please check one):

- □ I would like to avoid surgery (hysterectomy)
- □ I would like to delay surgery (hysterectomy)
- □ I would like to avoid other surgeries or procedures (such as myomectomy or uterine artery embolization)
- □ I would like to delay other surgeries or procedures (such as myomectomy or uterine artery embolization)
- □ I prefer taking medication rather than surgery or procedures until I enter menopause when my symptoms, such as heavy menstrual bleeding, should improve and gradually go away
- □ I would like to get pregnant after participating in the study
- \Box I don't know why
- \Box I don't want to answer
- □ Other: _____

[figure not shown]
Appendix F. Physician Surgery Questionnaire Version 1.0 – SAMPLE

Based on this subject's current presentation/profile as it relates to uterine fibroids, is surgery or surgical procedure one of the potential treatment options you would consider?

Yes No

If yes, which surgery or surgical procedure would you consider? Check all that apply.

Hysterectomy Myomectomy Uterine Artery Embolization Other _____

Appendix G. Uterine Bleeding Questionnaire (UBQ) – Treatment Period – SAMPLE

(To be Completed by Site Staff)

Version 2.0

During site visits in the Treatment Period, subjects who **did not** return a Sanitary Product Collection Keg (for menstrual blood loss analysis) will be asked whether they had any uterine bleeding or spotting since their last study visit.

[figure not shown]
1. Did the subject have any bleeding or spotting since her last study visit?

 \Box No \Box Yes

If yes, why were sanitary products not collected/returned? (Please select one response)

- □ Subject only had spotting that did not require the use of sanitary products*
- $\hfill\square$ There was no visible blood on sanitary products*
- □ Subject forgot to/did not collect*
- □ Subject/Site discarded the sanitary products*
- $\hfill\square$ Subject is still bleeding/spotting; will return when bleeding/spotting complete
- □ Subject collected sanitary products and did not bring them to this visit; will return sanitary products at a later date
- \Box Other

* If this response is checked, remind subject to collect and return all used or worn sanitary products with or without visible blood.

Appendix H. Uterine Bleeding Questionnaire (UBQ) – Post-Treatment Follow-Up Period – SAMPLE

(To be Completed by Site Staff)

Version 2.0

[figure not shown]
Subjects who have not returned sanitary products for their first full menses in the Post-Treatment Period, will be asked at the Post-Treatment Phone and Site Visits whether they had any bleeding or spotting since their last site or phone visit. Once a subject returns sanitary products for a full menses in the Post-Treatment Follow-up Period, this questionnaire no longer needs to be completed.

1. Did the subject have any bleeding or spotting since her last study visit (Site visit or phone visit)?

□ No □ Yes

If yes, why were sanitary products not collected/returned? (Please select one response)

- □ Subject only had spotting that did not require the use of sanitary products*
- $\hfill\square$ There was no visible blood on sanitary products*
- □ Subject forgot to/did not collect*
- □ Subject/Site discarded the sanitary products*
- □ Subject is still bleeding/spotting; will return when bleeding/spotting complete
- □ Subject collected sanitary products and did not bring them in yet; will return sanitary products at a later date
- \Box Other
- * Subject will be required to collect sanitary products for her next full menses.

